A modal window titled "Create New Mobile Worker" is open. It has a "Basic Information" section. The "Username*" field is highlighted with a yellow background, and a red arrow points to it from the right. A validation message below the field states: "✗ Username may not contain special characters." The "First Name" field is partially visible below the username field. To the right of the first name field, there is a placeholder image area with a red arrow pointing to it, and the message "✗ The picture can't be displayed".

Managing Users: Edit Mobile Workers

 The picture can't be displayed.

Managing Users: Edit Mobile Workers

 The picture can't be displayed.

[figure not shown]

Managing Users: Edit Mobile Workers

 The picture can't be displayed.

Managing Users: Edit Mobile Workers

[figure not shown]
Managing Users: Edit Mobile Workers

Managing Users: Case Sharing

5. The default in CommCare is that cases can only be accessed by the Mobile Worker who registered them
6. In order for all Mobile Workers to access all cases in the system, permission must be granted
7. This is accomplished by putting all mobile workers in an “All Mobile Worker” group and allow that group “case sharing” privileges

Managing Users: Case Sharing

Managing Users: Case Sharing

Managing Users: Case Sharing

 The picture can't be displayed.

Managing Users: Case Sharing

 The picture can't be displayed.

1. Once the group is set up and case sharing is turned on, you can add the mobile workers you have created.

Managing Users: Case Sharing

 The picture can't be displayed.

2. Once the group is set up and case sharing is turned on, you can add the mobile workers you have created.
3. Whenever you add a new Mobile Worker, you can add them to the case sharing group here or by editing their information directly.

Managing Users: Edit Mobile Workers

 The picture can't be displayed.

Understand:

1. After creating a new mobile worker, add them to the All Mobile Workers group

Managing Mobile Worker Performance

1.

R The picture can't be displayed.
1 n submissions
2 submissions
3 nitted
4 case activity
5 times

Time to try!

<https://www.commcarehq.org/a/txtxt/dashboard/project/>

[figure not shown]
1. Login to CommCare as a Web User
2. Create a Mobile Worker
3. Add them to the “All Mobile Workers” case sharing group

Web User

Creating a Web User

Basics of HQ: Users

In the Use

; have access to

Basics of HQ: Users

In the Use

[figure not shown]

Users have access to

Managing Users: Creating a Web User

[figure not shown]

Managing Users: Creating Web User

Web User will receive an email inviting them to join the project and create a password

Managing Users: Web User Role

The picture can't be displayed.

Click to define a role's parameters

Click to choose the levels of access on HQ and the reports that each type of role can access.

The picture can't be displayed.

The picture can't be displayed.

To the right of the role, you can also edit the specific access on HQ for each existing role

For example, you could create a unique role that would be constant across organizations

 The picture can't be displayed.

[figure not shown]
A Web User with Admin capabilities can remove the membership of other Web Users by clicking “Remove Membership” on the Web Users and Roles page.

Time to try!

<https://www.commcarehq.org/a/txtxt/dashboard/project/>

1. Login to CommCare as a Web User
2. Create a Web User
3. Make sure their User Rights are accurate

Web User: Other FunctionsSending a Broadcast

Basics of CommCareHQ: Messaging

In the M

 The picture can't be displayed.

[figure not shown]
1
2

egistered participants

Finishing Client Registration

[figure not shown]
1. Navigate to

Messaging > Contacts > Case Groups

Finishing Client Registration

2. Add every new case to the “All Participants” group using their caseID or phone number

[figure not shown]
Messaging: Broadcasts

1. Allows you

1. Me
2. Ca

you added their number to their profile)

Messaging: Broadcasts

Messaging: Broadcasts

[figure not shown]
Messaging: Broadcasts

Messaging: Broadcasts

[figure not shown]
Messaging: Broadcasts

Messaging: Broadcasts

Messaging: Broadcasts

Technical Issues

Most Common Issues

Issues

3. Conflation of Web User/MobileWorker roles

Solutions

4. Only give those that **needadmin** access a Web User account

5. (Re)Train staff on different credentials and dashboards

Most Common Issues

Issues

6. Texts are not sending

[figure not shown]
Solutions

7. Confirm the phone number
8. Confirm end date
9. Confirm the ptpt has not stopped texts
10. Check Message History, Message Log, ScheduledMessage Events

1 Most Common Issues

weekly texts
begin same day,
daily do not

[figure not shown]
Technical Issues

[figure not shown]
Technical Issues

Technical Issues

Technical Issues: Reporting Issues

How does BHC request the TXTXT App?

TXTXT App Set-Up

Your Clinic

TXTXT App Set-Up

1. Negotiate licensing fee with Dimagi
2. Set up license

TXTXT App Set-Up

1. Negotiate licensing fee with Dimagi
2. Set up license

TXTEXT App Set-Up

1. Negotiate licensing fee with Dimagi
2. Set up license

1. Gives you access to a “project space”
2. Make someone on your team a web user with “admin” access

TXTEXT App Set-Up

Your Clinic

1. Negotiate licensing fee with Dimagi
2. Set up license

Dimagi

[figure not shown]

1. Gives you access to a “project space”
2. Make someone on your team a web user with “admin” access

[figure not shown]
Your Clinic

TXTEXT App Set-Up

TXTEXT App Set-Up

TXTEXT App Set-Up

Your Clinic

1. Negotiate licensing fee with Dimagi
2. Set up license

Dimagi

1. Gives you access to a “project space”
2. Make someone on your team a web user with “admin” access

Your Clinic

1. Make [name] at Lurie a web user with “admin” access
[contact]
2. (optional) Any revisions to the encouraging messages

Lurie

1. Build/test your project space
2. Change your clinic’s web user access to “admin_noapps”

TXTEXT App Set-Up

Your Clinic

1. Negotiate licensing fee with Dimagi
2. Set up license

Dimagi

1. Gives you access to a “project space”
2. Make someone on your team a web user with “admin” access

Your Clinic

1. Make [name] at Lurie a web user with “admin” access
[contact]
2. (optional) Any revisions to the encouraging messages

Lurie

1. Build/test your project space
2. Change your clinic’s web user access to “admin_noapps”

Your Clinic

TXTEXT App Set-Up

Your Clinic

1. Negotiate licensing fee with Dimagi
2. Set up license

Dimagi

1. Gives you access to a “project space”
2. Make someone on your team a web user with “admin” access

Your Clinic

1. Make [name] at Lurie a web user with “admin” access
[contact]
2. (optional) Any revisions to the encouraging messages

Lurie

1. Build/test your project space
2. Change your clinic’s web user access to “admin_noapps”

Your Clinic

1. Add staff as mobile workers/web users
2. Start registering users

TXTEXT App Set-Up

You did it!

Go you!

2. Start registering users

APPENDIX C Eligibility Screener (Aim 1)

ELIGIBILITY SCREENING INTERVIEW

SCREENING DATE: _____
Month _____ Day _____ Year _____

STAFF INITIALS: _____ **SCREENING PHASE:** In Person | Phone
(Circle one)

Hi, My name is (name) and I'm one of the staff members working on the Midwest Treatment Text (TXTXT) project, which is being conducted in partnership with Midwest AIDS Education and Training Center (MATEC) and Lurie Children's Hospital of Chicago. This project will explore whether daily text message reminders can help adolescents and young adults living with HIV do a better job of taking their medications and staying in HIV care. Are you interested in hearing more about it?

Response: If yes, continue. If no, thank them for their time and discontinue screening.

Thanks for your interest in our project. As I just said, the purpose of the study is to explore whether daily text message reminders can help adolescents and young adults living with HIV do a better job of taking their medications.

If you are eligible and decide to enroll you will be asked to provide your cell phone number and to create a text message reminder for yourself. This personalized reminder will be sent to you daily, at a time that you decide. You will be asked to text back when you take your medications. You will also continue to meet with your medical provider. Additionally, we'll ask you to complete a computer-based questionnaire at your first visit. We'll also ask you to fill out the questionnaire again at 3 months and 6 months. You will be able to complete the survey online if you prefer you can also come into the clinic site to fill out the computer survey.

If you are eligible and decide to participate, we will keep all information we collect from you strictly confidential. We will need to ask you for contact information so that we can invite you back for various stages of the intervention.

To find out if you're eligible to participate in this project, I'll need to take less than 5 minutes to ask you some questions. Your answers to these questions will be kept confidential. That is, at this point, I will not be asking you any identifying information: I won't ask for your name, address, phone number or birthday. One of the reasons we stress confidentiality is that we do ask some very personal questions, and it is very important that you be as honest and as accurate as you can be with your answers. It is only if you are eligible and interested in participating that I will ask for your name and date of birth.

Are you willing to answer some questions to determine if you are eligible for the study?

Response: If yes, continue with Screening Questions. If no, ask for reasons why:

 No interest	01	 Afraid of research/guinea-pig	04
 Worried about anonymity	02	 Rather not say	05
 Study takes too long	03	 Other	06

If other, specify _____

Thank the participant for their time.

INSTRUCTIONS: This screening interview may be conducted in person or by phone. If eligibility is determined by phone, participants must make an appointment to reconfirm their answers to the screening questions in person before signing consent. Participant ID numbers will only be assigned (a) after the screening questions determine the volunteer to be eligible for this study and (b) after the participant signs the assent/consent form. Regardless of whether or not the participant is eligible, record the participant's responses to all questions.

RECRUITER INITIALS: _____

SCREENING DATE: _____

Month

Day

Year

1. First, how old are you?

_____ years (*If participant is not 16-35 yrs., check ineligible and continue*) Ineligible

2. What was sex assigned at birth?

Male

Femal

e

Interse

x

3. How do you self-identify in terms of

gender?Male

Female

Transgender woman

Transgender man

Other, Specify _____

4. Are you of Hispanic (Spanish) or Latino

origin?Yes

No

5. How do you describe your race or ethnic

background?Asian/Pacific Islander

Black/African American

Native American/Alaskan

NativeWhite

Latino/Hispanic

Multi-racial 5a) If "Multi-racial," specify _____

Other 5b) If "Other," specify _____

6. What is your preferred language?

English

Spanis

h

Other language, if "other", specify _____ (*Check ineligible and continue*)

7. Do you have a cell phone that can send and receive text messages?

Yes

No (*Check ineligible and continue*)

Ineligible

RECRUITER INITIALS: _____

SCREENING DATE: _____

Month

Day

Year

8. How often would you say you use your cell phone for sending or receiving text messages?

Never (*Check ineligible and continue*)

Ineligibl

1-2 times per week

3-5 times per

week Almost

every day Every
day

Several times a day

9. Have you ever been told by a doctor or other health care provider that you have HIV infection or have AIDS?

Yes

Ineligible

No (*Check ineligible and go to ineligible script*)

10. Have you ever taken antiretroviral medications or HIV

medications? Yes

Ineligible

No (*Check ineligible and go to ineligible script*)

11. Can you tell me when you started taking antiretroviral medications or HIV medications?

≤ 1 month ago (*Check ineligible and
continue*)

Ineligibl

but ≤ 6 months ago

but ≤ 24 months ago

24 months ago

12. Are you currently participating in any other research studies or programs about HIV treatment or medication adherence (support for taking your HIV medications)?

Yes (*Check ineligible and go to ineligible script*)

Ineligible

No

13. I need to know how you are doing with taking your HIV medications. Remember that this is a study for people who are having trouble taking their meds. Please answer as honestly as you can.

1. How many medication doses would you say you missed in the past 7 days? _____ doses

2. How many medication doses would you say you missed last month?

If a) is 1 or less AND b) is less than 3, check ineligible

Ineligible

Questions 14-18 are for the interviewer only.
**DO NOT ASK THESE QUESTIONS OF THE
PARTICIPANT.**

RECRUITER INITIALS: _____ SCREENING DATE: _____
Month Day Year

3. Does the volunteer appear to speak and understand English or Spanish?
 Yes
 No (*Check ineligible and continue*) Ineligible

4. Does the volunteer appear cognitively functioning and able to understand the assent/consent process?
 Yes
 No (*Check ineligible and continue*) Ineligible

5. Does the volunteer appear visibly distraught or emotionally unstable (i.e. suicidal, manic, exhibiting violent behavior)?
 Yes (*Check ineligible and continue*) Ineligibl
eNo

6. Does the volunteer appear intoxicated or under the influence of psychoactive agents?
Yes (*Check ineligible*)
 Ineligible
 No

7. Aside from eligibility criteria, does the volunteer appear to be a good fit for the project? Yes
 No (*Check ineligible and briefly explain below*) Ineligible

INSTRUCTIONS: If any of the above ineligible boxes are checked, read the INELIGIBLE script. If none of the ineligible boxes are checked, read the ELIGIBLE script below.

SCRIPT FOR INELIGIBLE VOLUNTEERS:

Participants for this project are selected based on the questions you were just asked. Based on your answers, it turns out you're not eligible to participate. Thank you for taking the time to talk with me about our project.

SCRIPT FOR ELIGIBLE VOLUNTEERS:

Thank you very much for the information you provided. Based on your answers to these questions, you are eligible to participate in this project. That means that if you want to participate in the text message project, you may. Do you think you might be interested in taking part in this project?

Response: If "NO", thank them for their time. If "YES":

Before we go any further, I need to get your name and birthdate, then schedule an appointment with you.

Participant Name*: _____ Date of Birth*: _____

Month Day Year

CONFIRM AGE GIVEN WITH DOB

* With the completion of this box, this document now contains confidential identifying information and should be securely filed with other confidential identifying records for this participant (e.g., Contact Information Sheet, Consent/Assent Form).

RECRUITER INITIALS: _____ **SCREENING DATE:** _____
Month Day Year

What's a good time for you to come in? _____ at _____ : _____ AM /PM

And if we miss you at that time, what's a good way to contact you to follow up? Phone:

What's your cell phone provider? _____

Ok to leave a voicemail message?

Just as a reminder, we need you to bring your cell phone with you to the visit because if you are randomly chosen to receive texts, we will test the text message system with your phone.

Email:

Ok to email?

Investigator/Designee

Signature

Print Name

Date

Entered into screening database

Screening ID: _____

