MATEC affiliated clinics in the Midwest region are eligible to participate in Aim 1 if meeting these criteria: (1) Clinic must have at minimum 40 current patients who are: racial/ethnic minority AND have a 'detectable' viral load AND are aged 16-35 years; (2) clinic must be willing to commit at least one staff person as lead for registering clients to receive the intervention, completing consent, and administering research surveys; (3) clinic must be willing to provide deidentified individual-level data for registered TXTXT participants, including viral load, retention in care (dates of clinic visits) at least twice per year; (4) clinic must not be using a competing medication reminder text messaging system; (5) clinic must be willing and able to rely on Lurie IRB. Once sites sign a memorandum of commitment, the study coordinator will schedule a conference call to conduct a standard of care questionnaire (Appendix K). The standard of care questionnaire will document existing clinic approaches to support adherence as well as any ancillary services (e.g., transportation assistance). This information will form a descriptive profile for each clinic.

Study Inclusion

For inclusion in the TXTXT intervention individuals must meet the following criteria: 1) diagnosed with HIV-infection and on ART regimen for at least one month (not new to ART); 2) aged 16-35 years; 3) have a viral load ≥ 200 c/mL and/or report poor adherence (<90% of pills taken in the last 30 days); 4) able to receive text messages; 5) provide informed consent for research component; and 6) are a patient of a participating clinic

Study Exclusion

Exclusion criteria includes: 1) those who are unable to give informed consent 2) those who are participating in other studies that impact primary and secondary outcomes.

Procedures for Recruitment and Informed Consent

Aim 1: Youth living with HIV (aged 16-35 years) who meet study inclusion criteria will be recruited by study staff from participating clinics. The EMR will identify potentially eligible patients who will be invited to complete further study screening and enrollment.

We will ask each clinic to construct a list of eligible patients and carefully track outreach, screening, and enrollment on an enrollment log provided. Clinics may enroll up to 50 participants (to account for 20% attrition, final sample of 40 participants per clinic).

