Participants will be contacted either by phone or in-person by staff members at participating clinics using the recruitment script/screener (Appendix C). If potential participants are interested in enrolling in the study (Aim 1), staff members at participating clinics which have received Institutional Review Board (IRB) certification will conduct eligibility assessment and consent conferences with participants. Potentially eligible participants will be contacted by clinic staff who will screen them for eligibility and further consent and enroll them if eligible (Appendix C). Those individuals who are ineligible will be thanked for their time.

Lurie Children's IRB will ensure that the consent forms meet institutional and funding source standards. Lurie Children's requires that research participants review and sign an informed consent form. Participants aged 16-17 years will sign an assent form (a waiver of parental consent will be obtained prior to study start). Participants aged 16-17 years are eligible to provide assent in all participating clinics. The informed consent forms include information about the overall purpose of the study, study procedures, potential risks, potential benefits to participating for individuals and society, alternatives to participating in the study, confidentiality of data, and contact information for the site's Principal Investigator and the IRB (Appendix L). Once informed consent has been obtained, the clinic staff will have the form reviewed by a fellow team member, who will confirm that it is fully completed before it is filed in a secure location under double-lock when not in use and with restricted access during work hours and/or when unattended.

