baseline	50 participants at each clinic	Participants at intervention clinics receive TXTXT	EMR data Baseline survey
		Participants at comparison clinics do not receive TXTXT (i.e., standard of care)	
3 months	50 participants at each clinic	Participants at intervention clinics continue with TXTXT	3-month survey
6 months	50 participants at each clinic	Participants at comparison clinics begin TXTXT TXTXT stops for all participants	EMR data 6-month survey
12 months	50 participants at each clinic		EMR data

Sampling

We will ask each clinic to construct a list of potentially eligible patients and carefully track outreach, screening, and enrollment on an enrollment log provided. Participants (N=600, n=50 per each clinic site) will be enrolled.

The list of potentially eligible patients will be constructed from available EMR data and will be queried based on: (1) diagnosed with HIV; (2) age range (16-35 years); (3) most recent viral load obtained in past 12 months. If potential participants meet the first two criteria, they will be evaluated based on (#3) viral load data. The following scenarios are possible: 1) potential participant is virally suppressed; 2) potential participant is viremic (>200 copies/mL); 3) potential participant does not have viral load data available. Patients who are viremic and meet criteria 1-3 (HIV status, age) will be considered eligible for study inclusion and will be called by clinic staff to confirm eligibility and assess interest. Patients who meet criteria 1 and 2 and are virally suppressed or missing viral load data will be contacted to assess eligibility - specifically, those who are virally suppressed will be queried about medication adherence (if <90% of pills taken in the past 30 days); for those who are missing viral load data they will be asked if they are willing to re-engage in HIV care and have labs drawn prior to enrollment (if so, they will follow steps outlined above for those with viral load

STUDY DESIGN AND DATA ANALYSIS

(VL) data). The list and eligibility assessment will be documented and reviewed on a weekly basis with individual sites to ensure timely enrollment into the study.

Data Analysis Plan and Variables

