Analysis of qualitative interview data will be led by [name]. Qualitative data will be audio recorded, transcribed verbatim then uploaded to Dedoose – a cloud-based flexible and adaptive qualitative analysis program.³⁸ After open coding 20% of the transcripts, [name] will create a codebook providing clear definitions and examples for each code. Transcripts will be analyzed using a directed content analysis approach.³⁹ The coding team ([name], [name]) will establish and maintain high inter-rater reliability (80% agreement).⁴⁰ Expert consensus (Drs. [name], [name], & [name]) will be used to address coder disagreements. This structured analysis uses existing theory and prior research to guide the identification of key concepts or thematic categories. After coding, Dedoose will be used to further categorize and visualize the data; organizing codes into frequency tables by participant and clinic descriptors to determine the occurrence and co-occurrence of codes in the sample.

Univariate analyses will be used to characterize and describe the sample and results from the quantitative survey.

RISKS TO HUMAN PARTICIPANTS (Aim 1 and Aim 2)

The largest risk to participants is a breach of confidential information.

In Aim 1, participants will be advised to delete the messages they receive from the Dimagi CommCare platform as a method of protecting the participant's HIV status. Participants will also be guided to select a personalized text message that does not disclose their HIV status ("remember to walk the dog", "you're your vitamins", "read your horoscope", etc.). Additionally, participants will walk through safe guarding their cell phones including how to activate passcodes and biometrics, as well as what to do if they lose their cell phone, get a new number, or switch providers (contact clinic study staff to update dimagi platform). Participants will also be advised that assessment questions may make them uncomfortable, however they can skip any question they choose not to answer.

In Aim 2, we will follow best practices to maintain confidentiality of participants, inclusive of staff and youth participants. Further, we will report findings in aggregate and will not use identifiers in qualitative quotes to ensure the identities of our participants remain confidential. In reporting qualitative findings, inclusive of quotes, we will use only study ID. Finally, we will not report back to clinics which staff or participants have enrolled in Aim 2.

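### Used by phone, the Appendix C recruitment script names AIDS and HIV before any step confirms that the listed patient is on the line and can talk privately

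*Combined protocol and SAP*

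**What the plan says.** Under Aim 1, Procedures for Recruitment and Informed Consent, the protocol states: "The EMR will identify potentially eligible patients who will be invited to complete further study screening and enrollment". The same section says that clinic staff make contact by phone or in person using Appendix C. Under Sampling, the first list criterion is an HIV diagnosis. Viremic patients on the list "will be called by clinic staff to confirm eligibility and assess interest", and patients who are suppressed or have no viral load result are contacted as well.

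Appendix C confirms the mode of use: "This screening interview may be conducted in person or by phone". It begins with the caller's own name and the project name, then names the Midwest AIDS Education and Training Center as a partner. Its second sentence says that the project will explore whether daily text reminders "can help adolescents and young adults living with HIV do a better job of taking their medications and staying in HIV care". Only after that does it ask whether the person wants to hear more.

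The script then tells the respondent that identifying details will not be requested at this stage: "It is only if you are eligible and interested in participating that I will ask for your name and date of birth".

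Under Risks to Human Participants (Aim 1 and Aim 2), the protocol says: "The largest risk to participants is a breach of confidential information".

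**The concern.** The call goes to a named patient whom the clinic already knows to have HIV. The text that staff are given to read mentions AIDS and then HIV care before anything establishes who is listening. If a relative, a housemate or the new holder of an old number answers, a call from a clinic about a project for young people with HIV makes the patient's status easy to guess.

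What is at stake is the harm that the protocol itself ranks first, at a moment before consent. It would also be hard to see afterwards. The acceptability survey in Appendix F asks only whether anyone learned the participant's status through the text messages, and people who are called but never enroll complete no survey at all.

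**Working it through.** No arithmetic applies. The check is to follow the phone contact in order and look for an identity or privacy step before HIV is first mentioned.

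| Order | Content of Appendix C | Identity or privacy check? |
|---|---|---|
| 1 | First sentence: caller's name, project name, AIDS training center as partner | None before it |
| 2 | Second sentence: project for young people living with HIV, medications and HIV care | None before it |
| 3 | Asks whether the person wants to hear more; stops if not | No |
| 4 | Fuller description; says name and birthday will not be asked at this point | No |
| 5 | Questions 9 to 13: HIV diagnosis, HIV medication, other HIV treatment or adherence studies, missed doses | No |
| 6 | Script for eligible, interested people: name and birth date taken | Stated age is compared with birth date; nothing is compared with the call list |

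Appendix C does require people screened by phone to reconfirm their answers in person before consent. That visit comes after the call, so it cannot protect the call.

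The safeguards elsewhere in the protocol were then checked for any that reach this first call:

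- **Discreet message wording** (Aim 1 recruitment procedures; Risks to Human Participants): covers texts chosen after enrollment.
- **Phone passcodes and lost phones** (Risks to Human Participants): advice to participants.
- **Private setting for assessments** (Adequacy of Protection against Risk): covers baseline and follow-up assessments.
- **Consent in a private room** (Aim 2 recruitment procedures): covers the consent conference.
- **Contact preferences in the tracking database** (Privacy and Confidentiality): covers people who have already given their preferences.
- **Staff training and confidentiality agreements** (Adequacy of Protection against Risk; Data and Safety Monitoring Plan): these do extend to recruitment and screening staff, but they are general and describe no step for opening a call.

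None adds a check of who has answered, or whether the person can speak freely, before the second sentence of the script. The gap therefore stands on the text. It concerns phone use; in-person screening is much less exposed.

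**The case against.** The strongest reply is that Appendix C is a screening interview addressed to the candidate, written for use both face to face and by phone. It is silent on how a call is opened, and silence does not mean that staff read it to whoever picks up. The callers work at the patient's own clinic and are trained in confidentiality and in screening technique. They may well ask for the patient first. Appendix M also counts staff hours for reviewing SOPs, which are not part of the documents and could hold such a step. This stands as a limit on how often harm would occur. It does not fill the gap, because no passage requires or describes the step and the only recruitment wording supplied starts with AIDS and HIV.

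Delaying name and birth date also has a purpose. Answers are recorded for everyone screened, and the form becomes an identifying record only once the name and birth date box is filled. Forms of ineligible people thus stay unnamed. That stands, and a repair must preserve it.

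A reader might infer several stronger things that the documents do not support:

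- **That the opening reveals the patient's diagnosis outright.** It describes a project for people with HIV and does not say that the person called has it. A listener would have to infer it.
- **That the script forbids early verification.** It says what will not be asked at that point in the interview. It does not bar asking for the listed patient before the interview starts.
- **That it falsely promises anonymity.** It promises confidentiality and says which details will be asked later.
- **That voicemail permission comes too late.** That question follows one about reaching the person after a missed appointment. No passage tells staff to leave a first-contact voicemail.
- **That a number of disclosures can be derived from planned enrollment and reach.** The documents give neither the phone share nor a third-party answer rate, so any count would rest wholly on assumption.

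**Conclusion.** The point holds as a gap in the phone procedure: HIV is mentioned before identity and privacy are checked, and a third party who answers could infer the patient's status. Its frequency cannot be estimated from the documents. The conclusion assumes that some first contacts are made by phone, which the protocol expects, and that staff follow Appendix C as written. Whether a parent might answer for a participant aged 16 or 17, who enrolls under a waiver of parental consent, is a reasonable worry, but the documents do not say whose number is called.

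This is a participant-protection matter with no bearing on the estimand, the eligibility rules or the analysis. It deserves action because the harm is the one the protocol ranks highest, a disclosure cannot be undone, and the repair is cheap.

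**What to change.** For phone use, place a short opening before the present first sentence of Appendix C:

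1. Ask for the patient by name, without mentioning HIV, AIDS, treatment or the project name.
2. Confirm identity verbally against the clinic list.
3. Ask whether this is a private time to talk; if not, arrange another time.
4. Only then read the project description and the screening questions.

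State that no first-contact voicemail may name the project or HIV.

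Keep the identity check verbal and do not write it on the screening form, so that forms of ineligible people remain unnamed as Appendix C intends. Because a verbal check would sit awkwardly beside the present statement that name and birthday will not be asked, reword that statement: identifiers will not be recorded with the answers unless the person is eligible and interested.

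If a site SOP already contains such an opening, copy it into Appendix C so that every clinic uses it. The cost is about one revised page, an IRB amendment and a little more time per call.
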